The experimental protocol for this study consists of two testing sessions. The following procedures are common to the Strength Group and the Fatigue Group in session 1. Upon arrival to the INPL the investigators will explain the protocol and received signed informed consent from the participants. Participants will also complete the Fatigue Severity Scale (FSS) and the Beck's Depression Inventory (BDI) questionnaires. Body composition will be assessed via Dual-Energy X-Ray Absorptiometry (DXA) utilizing standard guidelines set forth by the Department of Health and Exercise Science. Following consent, questionnaires, and DXA each participant will be in procedures specific to their randomized group. Group 1 = strength testing, tDCS → Sham; Group 2 = strength testing, Sham → tDCS; Group 3 = fatigue testing, tDCS → Sham; Group 4 = fatigue testing, Sham → tDCS

Strength Group Session 1

After completion of the questionnaires participants will begin strength testing of the knee extensors/flexors, planter/dorsi flexor muscle groups. The participants will perform these measurements while seated with the hip, knee, and ankle at 90 degrees of flexion. All procedures, including those for the fatigue group, will be performed with the participants in this position. Between muscle group testing and tDCS application participants will be allowed to get up and stretch as needed. A strap attached to a linear force transducer (Noraxon, Scottsdale AZ, USA) will be placed around the participant's ankle or metatarsals. Once in the proper position participants will be verbally encouraged to increase to maximal isometric force output over 3 seconds, continue maximal isometric force output for 1-2 more seconds, and then relax. After each maximal voluntary contraction (MVC) the participants will recover for no less than 60 seconds. Each muscle group will be tested 3-5 times, or until there is no further increase in force produced or if force produced is lower than the previous trial. Both the right and left legs will be tested.

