Once the leg motor cortex of the more-affected side (left or right) has been identified via TMS, a tDCS device (Neuroelectrics Inc., Simi Valley, CA, USA) will deliver a small direct current through two sponge surface electrodes (3cm × 3cm, soaked with 15 mM NaCl)(Dundas et al. 2007). The anodal electrode will be placed over the representation of the motor cortex for the more affected leg, and a second electrode will be placed on the forehead above the contralateral orbit. The intensity of the tDCS will be 2 mA applied for 10 minutes, starting at 0 and increasing to 2 mA over a 30 second period of time. At the 9:30 time point the current will gradually be reduced from 2 mA to 0 mA. Anodal tDCS with these parameters has been reported to change the excitability of the leg motor cortex without inducing side effects (Jeffery et al. 2007). The used parameters are in accordance with a safety criterion and far below the threshold for tissue damage (Nitsche et al. 2003). The voltage during tDCS application will be less than 10 V. During the application of the tDCS current participants will perform strength testing for more-affected side using the same procedures as the initial MVC acquisition. All MVC will be collected within the 10 min tDCS stimulation time. Participants receiving a sham condition will only receive the initial 30 seconds of stimulation, after which the current will be set to 0. These parameters for sham stimulation were chosen based on previous reports that the perceived sensations on the skin, such as tingling, usually fade out in the first 30 s of tDCS (Nitsche et al. 2003; Paulus, 2003). The participants and the investigator performing the MVC testing will be blinded to the tDCS condition. Participants will not be told their strength values until the end of all testing sessions.

After completion of the tDCS/Sham strength assessment participants will perform a 6 minute walk test. The test will be performed in a cordoned off hallway with 2 cones placed 30 meters apart. Once the participants begin walking, a timer will be started and the distance covered every min will be recorded. Participants are allowed to stop and rest during the test if required. Every minute during the walk test participants will be asked their rating of perceived exertion (RPE, 0-10 scale) (Dalgas et al. 2014)

Strength Group Session 2

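### The strength test during stimulation cannot fit its 10-minute window if it covers four muscle groups with at least three contractions each

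*Combined protocol and SAP*

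**What the plan says.** All of this comes from the protocol, section 2a (Study Procedures), Strength Group Session 1, unless stated otherwise.

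- **Initial test.** It is described as "strength testing of the knee extensors/flexors, planter/dorsi flexor muscle groups", which makes four muscle groups. Force rises over 3 s and is held for a further 1 to 2 s.
- **Recovery.** "After each maximal voluntary contraction (MVC) the participants will recover for no less than 60 seconds".
- **Trials.** "Each muscle group will be tested 3-5 times", followed by the qualification "or until there is no further increase in force produced or if force produced is lower than the previous trial".
- **Test during stimulation.** While the current is applied, "participants will perform strength testing for more-affected side using the same procedures as the initial MVC acquisition". Then: "All MVC will be collected within the 10 min tDCS stimulation time".
- **Second visit.** Strength Group Session 2 repeats the Session 1 procedures with the conditions swapped.
- **Risk section.** Section 9b, item 4, lists strength tests of the leg extensors, flexors and dorsiflexors. The plantar flexors are not in that list.

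The available text gives no shorter list of muscle groups, no cap on trials, no testing order for the test during stimulation, and no rule for what happens when 10 min run out. Section 2a refers to an attached timeline, which was not available for this review.

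**The concern.** Strength under tDCS against strength under sham is the central comparison in this arm. If the stated rules cannot all be kept, staff must relax one of them. They could let contractions run past the end of the current, cut recovery below 60 s, drop trials, or leave a muscle group untested. Each choice changes what is measured: a best-of-two value is not the same quantity as a best-of-five, and a contraction after the current has ended is not a during-stimulation value. If the choice differs between a participant's two visits, the within-person contrast also picks up a difference in procedure.

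**Working it through.** **Inputs** (section 2a): 4 muscle groups, one leg, contraction length c = 3 + 1 = 4 s to 3 + 2 = 5 s, recovery of at least 60 s after each MVC, window 600 s. The protocol shows no calculation behind the 10 min, so there is no derivation to reproduce.

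**Formula.** For k MVCs, with no recovery counted after the last one:

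T(k) = k × c + (k − 1) × 60 s.

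This is a lower bound, because 60 s is a minimum and no time is added for moving the strap or changing position.

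| k | Groups × trials | T(k) | Against 600 s |
|---|---|---|---|
| 8 | 4 × 2 | 452–460 s (7.5–7.7 min) | fits |
| 9 | 3 × 3 | 516–525 s (8.6–8.8 min) | fits |
| 10 | 2 × 5 | 580–590 s | fits |
| 11 | – | 644–655 s | over by 44–55 s |
| 12 | 4 × 3 or 3 × 4 | 708–720 s (11.8–12.0 min) | over by 108–120 s (1.8–2.0 min) |
| 15 | 3 × 5 | 900–915 s (15.0–15.3 min) | over by 300–315 s |
| 16 | 4 × 4 | 964–980 s | over by 364–380 s (6.1–6.3 min) |
| 20 | 4 × 5 | 1220–1240 s (20.3–20.7 min) | over by 620–640 s (10.3–10.7 min) |

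For example, k = 12 gives 12 × 4 + 11 × 60 = 708 s and 12 × 5 + 11 × 60 = 720 s. Capacity at the stated recovery is therefore 10 MVCs.

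**Recovery needed to force 12 MVCs into the window:** (600 − 12c)/11 = 50.2 s at c = 4 and 49.1 s at c = 5, both below the stated minimum.

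**What the stopping clause can do.** Suppose it can end a group at trial 2. With four groups the total must be 10 or fewer. If only one group stops at trial 2 and the other three reach trial 3 or later, the total is at least 2 + 3 × 3 = 11, which does not fit. So at least two of the four groups must stop at trial 2. That is necessary but not sufficient: 2 + 2 + 3 + 3 = 10 fits, whereas 2 + 2 + 3 + 4 = 11 does not.

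**The case against.** Four arguments on the other side carry weight.

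1. **The trial count may fall below three.** If the stopping clause overrides the 3-to-5 range, a four-group test can end in 7.5 to 7.7 min. As an illustration only, take trials as exchangeable, with no learning or fatigue. A group then stops at trial 2, 3, 4 or 5 with probability 1/2, 1/3, 1/8 or 1/24, and the total is 10 or fewer in about 46% of sessions. This stands, and it makes the conflict conditional. But the clause responds to force and not to the clock, so it cannot guarantee the window.

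2. **The reference to the same procedures may mean technique, not all four groups.** The fatigue group uses the same methods on the knee extensors alone, and the TMS hotspot is located for the leg extensors. Two groups would fit even at five trials each. This is a fair inference, but the fatigue section names its muscle and the strength section does not. With the three groups of section 9b, three trials each fits, but four or five does not.

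3. **Recovery might apply only within a muscle group.** Three trials in four groups would then take 12 × 4 + 8 × 60 = 528 s to 12 × 5 + 8 × 60 = 540 s. That contradicts the wording, which attaches recovery to every MVC, and it fails at four trials (16 × 4 + 12 × 60 = 784 s or more).

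4. **The timeline attachment may settle the sequence.** It may, so the finding is limited to the text available.

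A reader might also infer more than the documents support:

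- *That sessions will run to 20.7 min.* This needs all four groups to reach a fifth trial despite the stopping clause.
- *That stretch breaks lengthen the test.* The text more naturally places them between the initial testing and the start of stimulation. Strap changes can be made during recovery.
- *That only nine MVCs are allowed because the current is at full strength for nine minutes.* The ramps are described as "starting at 0 and increasing to 2 mA over a 30 second period of time" and "At the 9:30 time point the current will gradually be reduced from 2 mA to 0 mA", but the protocol's window is the whole 10 min and no full-current limit is set.
- *That the overrun biases tDCS against sham.* The tester is blinded, both visits follow the same procedures, and nothing suggests that overrun would differ by condition. A late MVC is also not necessarily uninformative, since the walk test itself follows stimulation.

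**Conclusion.** The concern holds in conditional form. If the test during stimulation covers the four groups of the initial test and three trials is a floor, it cannot be done in the window: the overrun is at least 1.8 to 2.0 min, and more at four or five trials. If the stopping clause can act at trial 2, the window can be met with four groups, but only when at least two groups stop there and the total is 10 MVCs or fewer.

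The conclusion rests on 4 to 5 s contractions, recovery at its 60 s minimum, and no time for changing position. Those last two assumptions favour the protocol. The text leaves open which muscle groups are tested, whether three trials is a floor, and what gives way at 10 min. The defect is a set of instructions that may not all be achievable, and the resulting loss of comparability is a risk that the documents do not allow to be sized.

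**What to change.** Reconcile the initial-test description, the on-stimulation instruction (both in section 2a) and the risk list in section 9b on three matters: which muscle groups are tested during stimulation, whether three trials is a minimum, and the 10-min window.

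Then, for the test during stimulation:

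- Pre-specify a fixed number and order of MVCs, the same at both visits and in both conditions, that fits the stated window at the stated recovery. For illustration, two per group in four groups takes 452 to 460 s, which leaves 140 to 148 s of the 600 s.
- In any comparison with the pre-stimulation test, use the same number of trials from that test.
- Time-stamp each MVC from the start of stimulation or sham, and flag late ones by the same clock in both conditions.

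No change to the stimulation or to the recovery period is proposed. The cost is a wording change and one time-stamp per contraction. The downside is fewer trials per group than the stated range, or fewer muscle groups tested during stimulation.

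Timing matters. At the 2017 continuing review 1 of 20 strength participants had been studied, leaving 20 − 1 = 19. That count should not be read as the number a change would still reach. Amendment 3 had closed the strength group, although the investigator asked to keep it open, and the Event History lists a final form submitted on 07/12/2018. If enrolment has ended, the report should state which muscle groups were tested during stimulation, how many trials were made, and when.

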*** * * Purpose, Study Procedures, Background * * ***

Original Protocol Number (e.g., 07-226H)

Title (Please indicate if the protocol title is different from the proposal title)

Complete Sections 1 - 16. Specify N/A as appropriate. Do not leave any required sections blank.

1. Purpose of the study

a) Provide a brief lay summary of the project in <200 words. The lay summary should be readily understandable to the general public, and is, for example, what would be released to a newspaper if requested.

In this project we will be using non-invasive brain stimulation on people with multiple sclerosis (PwMS) to improve leg muscle function. Two groups of participants will be recruited. One group will perform strength testing with and without the brain stimulation. After completing the strength testing they will walk for six minutes to see if any increases in strength translate into improved mobility. The second group will perform a fatigue task, pulling against a wire at a low level of force, with and without the brain stimulation. This type of brain stimulation has been shown to transiently improve strength and fatigue measures in other populations, e.g. aged, Parkinson's, and improve cognitive abilities in people with multiple sclerosis. It is our hope that the increases in performance seen in other patient groups will also occur in people with multiple sclerosis. Future investigations will look to apply the non-invasive brain stimulation technique during physical rehabilitation to improve short and long term outcomes related to physical function.

b) What does the Investigator(s) hope to learn from the study?

We expect to show that transcranial Direct Current Stimulation (tDCS) is an effective method for improving neuromuscular function in PwMS. With this information we plan to investigate the concurrent use of tDCS and physical rehabilitation and identify if tDCS can increase the gains seen with traditional PT and if these improvements last longer compared to when only physical therapy is performed.

c) Proposed Start Date (may not precede IRB approval date):

Oct. 1, 2016

2.

Study Procedures (If this is a student project, the methods section of the thesis or dissertation proposal must be attached in section #16 - Attachment section.)

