After no less than 7 days, participants will return to the INPL to perform their final session. All procedures for Session 2 will be the same as in Session 1, except that participants who received tDCS will now receive sham stimulation and those that received the sham treatment will receive tDCS.

In all sessions both, participants and raters will be blinded to the intervention type. The experimenter who

will apply the intervention (real tDCS or Sham) will be different from the experimenter determining the outcome measures.

Fatigue Group Session 1

Once consent, questionnaires, and DXA have been completed, MVCs of the right and left knee extensors will be performed using the same methods stated before. After MVC performance participants will be asked which is their more-affected leg and this answer will be compared to the results of the MVC testing. Once the more-affected leg is determined the investigators will use the same TMS procedures as above to identify the more-affected leg's representation in the motor cortex. The anode tDCS electrode will then be placed in this spot, and stimulation will begin 5 min prior to the start of the fatigue task. After 30 secs the current will be lowered to 0 for the Sham group. The treatment group will receive stimulation until the end of the fatigue task or for an additional 15 min, whichever condition occurs first. tDCS blinding and procedures are the same as they are for the strength group. Both participant and investigator will be blinded to the treatment.

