The fatigue task will consist of the participants performing an isometric contraction of the knee extensors. Participants will be positioned with the hip, knee, and ankle of the more-affected leg at 90 degrees of flexion. Just prior to the initiation of the fatigue task the participant will perform 1 MVC, and 30% of this force output will be the target output of the fatigue task. Visual feedback will be provided on a computer monitor. Participants will perform the task until they can no longer generate the needed force (within 5% of the target value for 5 seconds), or they say they want to stop. At every 1 minute interval the participant will be asked to provide their rating of perceived exertion (RPE) based on the modified Borg 10 point scale. The required leg position will be monitored by visual inspection, and feedback will be given to the subject by the same investigators for all experiments. Immediately after task failure another MVC with the knee extensors will be performed to quantify the decline in strength.

Fatigue Group Session 2

After no less than 7 days, participants will return to the INPL to perform their final session. All procedures for Session 2 will be the same as in Session 1, except that participants who received tDCS will now receive sham stimulation and those that received the sham treatment will receive tDCS.

In all sessions both, participants and raters will be blinded to the intervention type. The experimenter who will apply the intervention (real tDCS or Sham) will be different from the experimenter determining the outcome measures.

Electromyography (EMG)

During all strength and fatigue testing EMG signals will be recorded with bipolar surface electrodes that will be placed over the vastus medialis oblique, vastus medialis longus, rectus femoris, vastus lateralis, and biceps femoris. The electrodes will be attached according to landmarks between the innervation zone and the end of the tendon (Rainoldi et al. 2004, 2007). The EMG signals will be amplified (x 2,000), band-pass filtered (13–1,000 Hz; Noraxon) and recorded on a computer.

b) Explain why human subjects must be used for this project.

The goal of this project is to determine if tDCS can increase leg muscle strength and fatigue resistance in people with MS. Therefore all clinical testing needs to be performed in the patient population that is being studied.

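### Should the fatigue-task load be set from an MVC taken before stimulation, rather than from one taken just before the task?

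*Combined protocol and SAP*

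**What the plan says.** Section 2a (Study Procedures, Fatigue Group Session 1) sets the order of each visit. First, "MVCs of the right and left knee extensors will be performed using the same methods stated before". That method, given under Strength Group Session 1, reads "Each muscle group will be tested 3-5 times, or until there is no further increase in force produced"; a trial weaker than the one before it also ends testing. In the fatigue groups these trials serve to check which leg is more affected; they do not set the load. After TMS mapping, "stimulation will begin 5 min prior to the start of the fatigue task". At the sham visit the current goes to zero after 30 seconds. At the active visit it runs until the task ends, or for a further 15 minutes if that comes sooner.

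The load rule is "Just prior to the initiation of the fatigue task the participant will perform 1 MVC, and 30% of this force output will be" the target. The task ends when force can no longer be held ("within 5% of the target value for 5 seconds") or when the participant asks to stop. One more MVC straight afterwards measures the loss of strength. Session 2 repeats everything under the other condition, so the target is set afresh.

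Section 2b names leg strength and fatigue resistance as two separate aims, and strength has its own two groups. The Study Endpoint item (2e) is answered N/A. Time to failure is implied by the end rule but never named as an outcome.

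**The concern.** The load is part of how the outcome is measured, and here it may respond to the treatment being tested. The protocol itself expects strength to move in this window. In the strength groups "All MVC will be collected within the 10 min tDCS stimulation time", and the lay summary (1a) says "This type of brain stimulation has been shown to transiently improve strength and fatigue measures in other populations". If that hope is met, the participant works against a heavier target, with a higher failure limit, at the tDCS visit than at the sham visit.

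Randomised order does not remove this, because the load follows condition and not period. Nor does blinding, because the target comes from measured force. A null or shorter time to failure under tDCS could then mean no benefit, or a real benefit tested against a heavier load. The text does not say in words which question is meant, although a pre-stimulation MVC from the same visit is available.

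**Working it through.** The plan gives no power, standard deviation or effect size for this outcome, so there is no figure to reproduce. The check is one of timing, load and interpretation.

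**1. Timing.** Stimulation starts 5 min before the task, and sham current is off after 0.5 min, so about 4.5 min before the task. An MVC performed immediately before the task therefore falls, on the natural reading, with current on at one visit and off at the other. This order is inferred: no sentence states it, and the timeline attachment is not part of the text.

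**2. Load.** Let MVC under active stimulation be (1 + g) times the unstimulated MVC; g is assumed.

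- Current rule: target = 30% × (1 + g) of unstimulated MVC, which is 30.0%, 31.5% and 33.0% for g = 0, 5% and 10%.
- Pre-stimulation rule: target = 30% / (1 + g) of current MVC, which is 30.0%, 28.6% and 27.3%.

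The current rule holds relative intensity constant and lets absolute force move. The alternative does the reverse.

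**3. Time to failure.** Assume time is proportional to (relative force)^-n with n = 1.5 to 2.5. If the strength gain carries through to sustained effort, time at the pre-stimulation load changes by (1 + g)^n - 1. If the gain shows only in the brief MVC, time under the current rule changes by (1 + g)^-n - 1. The table gives tDCS relative to sham, with no other effect of tDCS.

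| g | Sustained gain, current rule | Sustained gain, pre-stimulation rule | Brief gain only, current rule | Brief gain only, pre-stimulation rule |
|---|---|---|---|---|
| 0 | 0 | 0 | 0 | 0 |
| 5% | 0 | +7.6 to +13.0% | -7.1 to -11.5% | 0 |
| 10% | 0 | +15.4 to +26.9% | -13.3 to -21.2% | 0 |

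With n = 1 to 3, the sustained-gain figures under the pre-stimulation rule become +5.0 to +15.8% (g = 5%) and +10.0 to +33.1% (g = 10%).

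**4. What each rule leaves open.** Under the current rule, a null result with g > 0 does not exclude a benefit at fixed force. Under the pre-stimulation rule, a lengthening of 8-13% or 15-27% can arise from strength alone, so a positive result does not establish fatigue resistance. Either rule needs target force and the just-before-task MVC set out by condition before it can be read.

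**5. What the alternative would cost.**

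- The reference MVC would be separated from the task by TMS mapping plus 5 minutes. Section 2a lets participants get up and stretch between muscle testing and tDCS, so seating or strap placement may also differ.
- If the best of several trials set the load, it would exceed a single trial by 0.74 to 1.16 trial SDs, by simulation over readings of the stopping rule. With an assumed trial CV of 3-8% that is 0.74 × 3% = 2.2% to 1.16 × 8% = 9.3%, and times shorten at both visits by 1 - 1.022^-1.5 = 3% to 1 - 1.093^-2.5 = 20%.
- Visit-to-visit variation stays. With an assumed day-to-day CV of 3-10%, the SD of the difference in target is √2 × CV = 4.2% to 14.1%.

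**The case for a change.** The strongest case for a change is that the fatigue result is hardest to read in exactly the situation the protocol hopes for, and that a pre-stimulation MVC costs nothing extra to collect. With the endpoint item left at N/A, nobody has written down that the question is one of relative intensity. Tabulating target force shows that the load differed, but it does not recover time at a fixed force without an assumed force-time relation.

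The last two statements stand as limits on what the trial can claim: a null time to failure should not be presented as excluding a benefit at fixed force. They do not make the comparison unsound. A target defined as a fraction of the MVC taken at the task is a relative-intensity task by construction. That fits an aim which lists fatigue resistance apart from strength, because it stops a strength gain from passing as endurance. Time to failure understates a benefit only against an absolute-load question, which the protocol never asks.

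The 5% tolerance might seem to offer a documented threshold, since 1/0.95 - 1 = 5.3% is the MVC gain at which the tDCS-visit failure floor passes the sham-visit target. But that sets one visit's floor against the other visit's target. Compared floor with floor, any gain moves the limit in proportion, so 5.3% marks nothing.

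**Conclusion.** No change to the plan is needed. The load rule is a fair trade-off: it gives a sound comparison of tDCS and sham at 30% of current strength, and setting the load before stimulation would exchange one ambiguity for another with costs of its own. What the text leaves unsaid is detail that analysts fill sensibly. The just-before-task MVC has to be recorded to set the target, and it is the natural reference for the planned post-task decline in strength, so it would be shown by condition alongside time to failure.

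The difference between the two questions is zero if tDCS leaves MVC unchanged, and about 8-13% or 15-27% of time to failure at an assumed sustained MVC gain of 5% or 10% (n = 1.5 to 2.5). None of these inputs is in the documents. The conclusion also rests on the inferred order of MVC and stimulation; if the MVC were taken before current starts, the concern would fall away. The Event History lists a final form submitted on 07/12/2018; if testing had finished by then, a new load rule could not be applied in any case.
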